- n ECG print-outs: within 15 min before infusion start, at 10 min after infusion start, and, in case of conversion from AF, within 1 min after conversion BUT before infusion stop. Diagnosis of AF (defined as absence of discrete P waves and an irregular ventricular rate) to be confirmed based on a 12-lead ECG. On Day 2 the ECG should be completed 24 h +/- 2 hours after infusion start.
- o Continued assessment to start 30 min before infusion. Holter to stop after the PK sampling at 8 h. Telemetry to continue for minimum 8 h after infusion start.
- p Should be done in all patients; mandatory if not done within 6 months (inclusive) before randomisation.
- q Heart rhythm, LV size, LV area, LVEF, atrial area and size as well as other clinically significant finding results to be provided or requested if available.
- r In case of AF persistence at 90 min after start of infusion, a direct-current electrical cardioversion is to be done within 180 min post-infusion start (200 J biphasic synchronised).
- s Recording of any AEs/SAEs will start after the ICF has been signed. From infusion start, special attention should be paid to AEs related to the central nervous system including tremors.

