Every effort will be made by the investigator to assess the relationship of the AE, if any, to the study drug. Causality should be assessed using the categories presented in the following table:

Unrelated:	Clinical event with an incompatible time relationship to study drug administration, and that could be explained by underlying disease or other drugs or chemicals or is incontrovertibly not related to the study drug.
Unlikely:	Clinical event whose time relationship to study drug administration makes a causal connection improbable, but that could plausibly be explained by underlying disease or other drugs or chemicals.
Possible:	Clinical event with a reasonable time relationship to study drug administration, but that could also be explained by concurrent disease or other drugs or chemicals.

Probable:	Clinical event with a reasonable time relationship to study drug administration, and is unlikely to be attributed to concurrent disease or other drugs or chemicals.
Very	Clinical event with plausible time relationship to study drug administration, and that cannot be explained by concurrent disease or other drugs or chemicals.
Likely/Certain:	

Action Taken

The investigator will describe the action taken in the appropriate section of the eCRF, as follows:

- None
- Study drug stopped
- Study drug temporarily interrupted
- Concomitant medication
- Other, specify.

Follow-up of Adverse Events

All investigators should follow patients with AEs until the event is resolved or until, in the opinion of the investigator, the event is stabilised or determined to be chronic. Details of AE resolution must be documented in the eCRF.

Patients should be followed for 30 days after receiving the study drug, and any AEs that occur during this time should be reported according to the procedures outlined below.

Documentation and Reporting of Adverse Events

AEs should be reported and documented in accordance with the procedures outlined below. All AEs occurring during the study must be documented in the relevant eCRF pages. The following data should be documented for each AE:

- Description of the event
- Classification of “serious” or “not serious”
- Severity
- Date of first occurrence and date of resolution (if applicable)
- Action taken
- Causal relationship

- Outcome of event (unknown, recovered, not yet recovered, recovered with sequelae, death [with date and cause reported])

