10.2 Independent Data Monitoring Committee

Safety, tolerability, PK/PD and efficacy will be regularly reviewed by an unblinded independent DMC to advise on dose escalation, de-escalation, and study progression decisions at the interim analyses. The DMC will also periodically review accumulating safety, tolerability, efficacy and PK/PD data throughout the study.

At the end of Part 1, after up to 36 initial patients receiving AP30663 and placebo have completed Day 2 assessments of the study (or terminated the study), the DMC will be convened to review the accumulating unblinded efficacy (including ECG and Holter ECG), PK/PD, safety and tolerability data for the study in an interim analysis, and provide a recommendation on dose escalation, de-escalation, and study progression/early termination in case there is a concern regarding safety (see [Section 8.1](#)

for options regarding Part 2 study design). A pre-determined efficacy algorithm will be put in place to guide the independent DMC in its decision. Decision rules will be based on the AF conversion rate, safety and tolerability signals including but not limited to increase in QTcF interval and number and severity of local injection site reactions.

During the enrolment period, an IA may be planned on a reduced cohort if preliminary blinded safety and efficacy data indicate that current enrolment is sufficient for the DMC to provide a recommendation for Part 2.

Full details of composition, operational aspects, and data to be reviewed and recommendations to be made by the DMC will be described in the DMC Charter. Detailed decision rules will be outlined in the DMC Charter or the SAP.

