2.2. Timings of Analyses

The study will be conducted in two parts (Parts 1 and 2): Part 1 of the study is a fixed randomisation placebo-controlled parallel design, and Part 2 will be an adaptive design conducted in one or more further doses of AP30663 vs Placebo.

In Part 1 of the study, up to 36 patients will be randomised in a 1:1 ratio to receive AP30663 at 3 mg/kg or matching placebo. An interim analysis (IA) will be conducted once the randomised patients in Part 1 have completed Day 2 assessments or terminated the study (see section 8.1 of the protocol).

An interim analysis (Part 1) including efficacy, PK/PD, safety and tolerability data will be conducted after all randomised patients have completed Day 2 assessments of the study, in order to determine the starting dose(s) for Part 2 of the study. For further information see section 11. An independent data monitoring committee (DMC) will be convened to review the accumulating unblinded efficacy (including ECG and Holter ECG), PK/PD, safety and tolerability data for the study at the time of the interim analysis.

During Part 2, IAs will occur when 18, 36 and 54 patients have been randomised to open-doses including placebo, and have completed Day 2 assessments or terminated the study.

For Part 2, the DMC will give their recommendations regarding continuation or early termination of the study. Decision rules will be based on the AF conversion rate; however the DMC will also have the option to stop a dose arm (or the study) due to unacceptable safety and tolerability (including but not limited to increase in QTcF interval and number and severity of local injection site reactions).

An unblinded team (unblinded statistician and unblinded programming team) will be responsible for generating and delivering unblinded TFLs to the DMC members. Tables that will be delivered for the interim analysis are detailed in Section 16.

This document is confidential.

3. Study Objectives

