10.3. Adverse Events / Adverse Drug Reactions

AEs will be coded using the Medical Dictionary for Regulatory Activities (MedDRA) version 21.1 or an updated version. Summaries will be presented by system organ class (SOC) and preferred term. Treatment-emergent AEs (TEAEs) are defined as any AE occurring or worsening on or after the first dose of study medication. Partial AE dates will be imputed.

The frequency and incidence of TEAEs will be presented by SOC and preferred term for each treatment group (number and percentage of patients experiencing at least one TEAE per preferred term as well as the number of observed events per preferred term; percentages will be based on the number of patients in the safety set).

The summaries presenting frequency of AEs by SOC and PT will be ordered by overall descending frequency of SOC and then, within a SOC, by overall descending frequency of PT.

Separate tables will be presented by severity and by relationship, and for SAEs, related TEAEs, and TEAEs leading to study discontinuation.

Relationships of 'very likely', 'probable' and 'possible' are to be considered as related to study drug for the summary tables. Relationships of 'unlikely' and 'unrelated' are to be considered not related to study drug.

In case of missing relationships, AEs will be considered as related.

All AEs will be presented in full in a comprehensive listing including patient number, treatment group, severity, seriousness, action taken, outcome, relationship to treatment, onset/stop, and duration. TEAEs will be flagged in the listings.

This document is confidential.

Details of SAEs and AEs leading to withdrawal will be listed separately.

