Table 14.1.5.2	Compliance with Study Treatment	Safety Set	
Table 14.2.1.1.1	Conversion from AF within 90 Minutes from Start of Infusion : Summary of Response Rate, Bayesian Model	Full Analysis Set	✓
Table 14.2.1.1.2	Conversion from AF within 90 Minutes from Start of Infusion : Summary of Response Rate, Bayesian Model	Per Protocol Set	
Table 14.2.1.1.3	Conversion from AF within 90 Minutes from Start of Infusion : Summary of Response Rate, Logistic Regression	Full Analysis Set	✓
Table 14.2.1.1.4	Conversion from AF within 90 minutes from start of infusion : Summary of Response Rate, Logistic Regression	Per Protocol Set	
Table 14.2.2.1.1	Time to Conversion from AF – Descriptive Statistics, Kaplan-Meier Analysis	Full Analysis Set	✓
Table 14.2.2.1.2	Time to Conversion from AF – Descriptive Statistics, Kaplan-Meier Analysis	Per Protocol Set	
Table 14.2.2.2.1	Relapse of AF within 5 min following Pharmacological or DC Conversion – Summary of relapse rate - Logistic Regression	Full Analysis Set	
Table 14.2.2.2.2	Relapse of AF within 5 min following pharmacological or DC conversion – Summary of relapse rate	Per Protocol Set	

This document is confidential.

Table Number	Name	Analysis Set	Delivered for Interim analysis/DMC
Table 14.2.2.2.3	Relapse of AF within 5 min following Pharmacological Conversion – Summary of relapse rate - Logistic Regression	Full Analysis Set	
Table 14.2.2.2.4	Relapse of AF within 5 min following Pharmacological Conversion – Summary of relapse rate - Logistic Regression	Per Protocol Set	
Table 14.2.2.3.1	Proportion of Patients in SR after Start of Infusion at Different Timepoints - Logistic Regression	Full Analysis Set	✓
Table 14.2.2.3.2	Proportion of Patients in SR after Start of Infusion at Different Timepoints - Logistic Regression	Per Protocol Set	
Table 14.2.3.1	Descriptive Statistics of Plasma Concentration over Time by Treatment	PK Set	
Table 14.2.3.2	Summary of Pharmacokinetic Parameters – NCA Approach	PK Set	
Table 14.3.1.1	Overall Summary of Treatment-Emergent Adverse Events	Safety Set	✓
Table 14.3.1.2	Treatment-Emergent Adverse Events by System Organ Class and Preferred Term	Safety Set	
Table 14.3.1.3	Treatment-Emergent Adverse Events Related to Study Treatment	Safety Set	✓
Table 14.3.1.4	Serious Treatment-Emergent Adverse Events by System Organ Class and Preferred Term	Safety Set	✓
Table 14.3.1.5	Treatment-Emergent Adverse Events Leading to Study Discontinuation by System Organ Class and Preferred Term	Safety Set	

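### At the Part 2 interims the DMC's adverse event tables have no common time window, so events starting after Day 2 are under-counted for a newly opened dose

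*SAP*

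**What the plan says.** **Trigger.** SAP 2.2 counts the patients who "have been randomised to open-doses including placebo, and have completed Day 2 assessments or terminated the study", at 18, 36 and 54 patients in Part 2. Day 2 is about one day after dosing; the Protocol 8.1.2 footnote reads "On Day 2 the ECG should be completed 24 h +/- 2 hours after infusion start".

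**Collection period.** Protocol 10.1.3.1: "Patients should be followed for 30 days after receiving the study drug, and any AEs that occur during this time should be reported".

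**Counting rule.** SAP 10.3 treats an event as treatment-emergent if it starts or worsens at or after dosing, with no upper time limit. For the table by system organ class and preferred term it adds "percentages will be based on the number of patients in the safety set". SAP 6.1 presents summaries by treatment and overall, so placebo is a single column across cohorts.

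**What the DMC receives.** SAP Section 16 ticks three TEAE tables for the interims: overall summary (14.3.1.1), related (14.3.1.3) and serious (14.3.1.4). Only disposition and demographics have a cohort-only interim version. The AE and SAE listings in Section 18 are not ticked. Extent of exposure in SAP 10.1 means infusion duration and volume, not time under observation. The SAP specifies no fixed window, person-time rate or time-to-event method for adverse events.

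**The concern.** A crude percentage compares arms fairly only if the arms have been observed for similar lengths of time. Here they have not. 3 mg/kg closes at the end of Part 1, and most placebo patients at each Part 2 interim predate the current cohort, so these groups will normally have completed their 30 days. A newly opened dose consists entirely of patients from the latest cohort, the last of whom has about one day of follow-up. An event starting in week 2 or 3 is counted almost fully for the comparators and only partly for the new dose. The same mismatch returns whenever a dose opens, and always in the same direction.

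The DMC may stop an arm for safety or tolerability (SAP 2.2), and a new arm may have only 12 patients. In the package that the SAP lists, the DMC sees neither onset dates nor time at risk by arm for these events, so it cannot make the adjustment itself.

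**Working it through.** **Step 1. Arm sizes, checked against the plan's own example.** Part 1 is 1:1 with up to 36 patients, giving 18 placebo and 18 on 3 mg/kg. A Part 2 cohort of 18 at 2:1 adds 12 active and 6 placebo. At N = 54, placebo = 18 + 6 = 24 and 5 mg/kg = 12, as in Example 1 of Protocol 17.3 (3/24 and 8/12). The posterior Beta(1+8, 1+4) gives Pr(P > 0.65) = 0.499, matching the stated 0.50. The documents state no follow-up or AE-rate figure, so there is none to reproduce.

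**Step 2. Placebo patients enrolled before the current cohort.** 18/24 = 75%, 24/30 = 80% and 30/36 = 83% at the three Part 2 interims.

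**Step 3. Follow-up of the newest cohort.** Assumptions, none of them in the documents: 18 patients enrol evenly over T days; the data cut falls one day after the last infusion; earlier cohorts have completed 30 days. A patient enrolled at day u then has follow-up f = min(30, T − u + 1). For T = 30 the values run from 1 to 30 days with mean 15.9, and 1 of 18 patients has reached Day 30.

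**Step 4. Expected percentages when the arms are equally safe.** Assume a 30-day risk of 20% in every arm at constant hazard: h = −ln(0.8)/30 = 0.00744 per day.
- New dose: mean of 1 − exp(−h·f) over the cohort.
- 3 mg/kg: 20%.
- Pooled placebo at the first Part 2 interim: (18 × 20% + 6 × new-dose value)/24.
- Shortfall in patients: 12 × (20% − new-dose value).

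| T (days) | Mean follow-up, new cohort (days) | At Day 30 | New dose | Pooled placebo | 3 mg/kg | Shortfall in 12 patients |
|---|---|---|---|---|---|---|
| 14 | 8.0 | 0% | 5.7% | 16.4% | 20% | 1.7 |
| 30 | 15.9 | 6% | 11.0% | 17.7% | 20% | 1.1 |
| 60 | 22.6 | 50% | 15.2% | 18.8% | 20% | 0.6 |
| 90 | 24.7 | 67% | 16.6% | 19.2% | 20% | 0.4 |
| 180 | 26.9 | 83% | 18.0% | 19.5% | 20% | 0.2 |

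**Step 5. Sensitivity.**
- Assumed risk of 10% to 40%: the shortfall runs from 3.3 patients (T = 14, 40%) to 0.1 (T = 180, 10%).
- Data cut 14 days after the last infusion, 20% risk: 0.3 patients at T = 30 and 0.2 at T = 60.
- Adding a 30% infusion-day risk, equal in all arms and fully captured: the new dose shows 37.7% against 1 − 0.7 × 0.8 = 44.0% for 3 mg/kg at T = 30, and 42.6% against 44.0% at T = 180.

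**Step 6. With a common window.** If events are counted only up to Day 2 in every arm, equally safe arms have an expected difference of zero, whatever the accrual.

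**The case against.** The strongest reply is that what matters most for this drug happens on the infusion day. Treatment is one 30-minute infusion. Protocol 8.2.1 reports that the QTcF effect had returned to baseline by 8 hours at 6 mg/kg. The DMC's named signals are QTcF and local injection site reactions. QTcF effects, and any site reaction starting by Day 2, are captured equally in every arm, and ECG and vital-sign tables and listings also go to the DMC. This stands. A reader might infer that a new dose must look safer by construction; the documents do not support that, because a dose with more acute toxicity can still look worse. Nor is one day the typical follow-up: it is that of the last patient only.

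A second reply is that the DMC is not blind to maturity. The cohort-only disposition table (14.1.1.2) shows how many of the current cohort have completed the study, by treatment. Protocol 10.2 adds "The DMC will also periodically review accumulating safety, tolerability, efficacy and PK/PD data throughout the study", so late events can surface afterwards, and it leaves the data to be reviewed to a DMC Charter that is not among these documents. This stands in part. A completion count does not correct a percentage, and SAP 2.2 itself names Section 16 as the place where the interim tables are detailed.

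Third, the effect is small beside chance: the standard error for 12 patients at 20% is √(0.2 × 0.8/12) = 11.5 points, against a gap of 20.0 − 11.0 = 9.0 points at T = 30. That is true, but the gap is systematic and avoidable.

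Fourth, the denominator sentence in SAP 10.3 describes the table by organ class and preferred term (14.3.1.2), which is not ticked for the DMC. Applying it to the three ticked tables is an inference, though a reasonable one, since no other rule is given for them.

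A reader might also extend the point to Table 14.2.2.3.1 ("Proportion of Patients in SR after Start of Infusion at Different Timepoints - Logistic Regression"), which also goes to the DMC. That does not follow. SAP 14.2.5.2 sets the default denominator to patients with an observation, so a partly filled Day 30 row is imprecise but not deflated. Removing it would withhold valid data.

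**Conclusion.** The point holds for adverse events that start after Day 2, at the Part 2 interims, for a newly opened dose. Against 3 mg/kg the under-count is largest; against pooled placebo it is smaller, because 6 of the 24 placebo patients share the short follow-up. A dose carried over from an earlier cohort is less affected.

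The size depends on accrual, data-cut lag and AE risk, none of which the documents give. At an assumed 20% risk and a cut at the last patient's Day 2, it is about 1.1 patients in 12 for a 30-day cohort and below 1 for cohorts of 60 days or more. It also assumes that earlier cohorts have completed their 30 days by the interim, which is likely but not stated. The final analysis is unaffected, since every patient's 30-day period will then be over. This is a cheap improvement, minor to moderate in weight.

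**What to change.** In SAP 10.3 and Section 16, add interim/DMC versions of Tables 14.3.1.1, 14.3.1.3 and 14.3.1.4 restricted to TEAEs with onset from the start of infusion to the Day 2 visit, applied identically in all arms. Keep the all-follow-up versions beside them, with patient-days of follow-up, or the number of patients past Day 30, for each arm. State in SAP 10.3 that the Safety Set denominator applies to these tables too.

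One detail needs a line of text. Protocol 10.1.3.1 lists the date of first occurrence for each event but no clock time, so the window is best defined by date. The partial-date rule in SAP 6.3.2, now limited to treatment emergence, should be extended to it.

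Table 14.2.2.3.1 needs no change. The cost is SAP wording, one onset filter in existing programs and one more version of three interim tables. No new data are needed, and no dosing or stopping rule changes.

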10.4. Laboratory Evaluations

The haematology and clinical chemistry laboratory analyses will be performed at local laboratories. Reference ranges will be supplied by local laboratories and used by the investigator to assess the laboratory data for clinical significance and pathological changes. The following laboratory safety tests will be performed at the times outlined in the Study Procedures and Flowchart in Section 3.9.

Haematology

Haemoglobin, haematocrit, red blood cells (erythrocytes), white blood cells (leukocytes, total and differential), basophils, eosinophils, lymphocytes, monocytes, neutrophils, and platelets.

Clinical Chemistry

ALT, AST, bilirubin (direct, indirect, total), creatinine, gamma-glutamyltransferase, glucose (random), eGFR, urea (BUN), sodium, potassium, calcium, and magnesium.

Other Laboratory Variables

INR/APTT and TSH. These variables will be summarized and listed within clinical chemistry.

For all laboratory parameters, the following summary tables will be presented by visit and treatment for each test:

- Actual and changes from baseline for continuous variables
- Shift from baseline
- Number and percent of patients with clinically significant changes

All laboratory results in SI units will be included in data listings. Tests will be listed in alphabetical order. Abnormal lab values will be flagged in the listing.

10.5. Vital Signs

Vital signs will be recorded as indicated in the Study Procedures and Flowchart in Section 3.9. Blood Pressure, heart rate, and heart rhythm (from ECG) will be included and recorded in a standardized manner, *i.e.*, after the patient has rested in the (semi)supine position for 5 min and before blood sampling or laboratory tests. Vital signs measurements will be repeated in case of clinically significant abnormalities.

This document is confidential.

All vital signs (absolute values and change from baseline) will be summarized by visit, heart rhythm and timepoint for each treatment group.

All vital signs data will be listed chronologically by parameter and included in data listings.

10.6. ECG

A 12-lead digital ECG will be performed at the times outlined in the Study Procedures and Flowchart in Section 3.9 in a standardized manner (*i.e.* after the patient has rested in the [semi]supine position for at least 5 min).

The investigator will assess ECG abnormalities (e.g. ischemia, conduction abnormalities, and rhythm abnormalities) and define the ECG intervals as part of the screening of eligibility and according to the inclusion/exclusion criteria, and as part of an adverse event assessment.

12-lead digital ECG will be overread by the central ECG laboratory. The following measurements will be provided for all PK time points: RR, PR, QRS, QT, QTcF (Fridericia's correction of QT interval), heart rate, as well as T- and U-wave morphology classifications.

Bedside safety ECGs will be collected by the site, printed and reviewed by the investigator on site.

ECG intervals based on these safety ECGs will only be recorded if part of an adverse event.

A summary table for actual and change from baseline will be provided by treatment.

Results for 12-Lead ECGs will be summarized by the number and percentage within each category ("normal", "abnormal, not clinically significant", and "abnormal, clinically significant") .

Abnormal results for 12-Lead ECGs will be summarized as below:

- Absolute QTc interval prolongation:
 - QTc F interval > 450 ms
 - QTc F interval > 500 ms
- Change from baseline in QTc interval:
 - QTc F interval increases from baseline >30 ms
 - QTcF interval increases from baseline >60 ms

ECG data will be listed for all patients, and any clinically significant findings in ECG values will be flagged.

A cardiac Statistical Analysis Plan will be developed by Clario.

This document is confidential.

